#### **2.3 Exploratory Objectives**

- 2.3.1 To determine whether ASL-measured perfusion can identify treatment response (time to progression) earlier than the currently used RECIST criteria in patients undergoing IO.

#### **2.4 Endpoints**

Primary end points for this study will include the absolute days of progression free survival (PFS) and overall survival (OS). Additionally disease status (progression versus not) at 7 months and survival (dead or alive) at 24 months post-treatment initiation will also be documented. Progression will be determined based on the clinically accepted RECIST criteria.

### **3.0 Subject ELIGIBILITY**

Eligibility waivers are not permitted. Subjects must meet all of the inclusion and exclusion criteria to be registered to the study. Study treatment may not begin until a subject is registered.

**3.1 Inclusion Criteria (RCC Subjects)**

- 3.1.1 Diagnosis/disease status: Patients with locally advanced or metastatic renal cell carcinoma.
- 3.1.2 Patients scheduled to undergo anti-angiogenic treatment or IO.
- 3.1.3 Age  $\geq$  18 years.
- 3.1.4 Performance status: ECOG Status 0, 1 and 2.
- 3.1.5 Women of child-bearing potential must agree to undergo a urine pregnancy screening per standard Radiology departmental protocol, in place to prevent imaging of pregnant patients.
  - 3.1.5.1 A female of child-bearing potential is any woman (regardless of sexual orientation, having undergone a tubal ligation, or remaining celibate by choice) who meets the following criteria:
    - Has not undergone a hysterectomy or bilateral oophorectomy; or
    - Has not been naturally postmenopausal for at least 12 consecutive months (i.e., has had menses at any time in the preceding 12 consecutive months).
- 3.1.6 Ability to understand and the willingness to sign a written informed consent.

**Inclusion Criteria (healthy controls)**

- 3.1.7 Age  $\geq$  18 years.
- 3.1.8 Ability to understand and the willingness to sign a written informed consent.

**3.2 Exclusion Criteria**

- 3.2.1 Subjects may not be receiving any other anti-angiogenic agents, at the time of enrollment.
- 3.2.2 Subjects must not be pregnant since pregnancy is a contraindication to administration of gadolinium-based contrast agents.
- 3.2.3 Any contraindication to MRI per Radiology Department's routine protocol, e.g. MRI-incompatible objects, including but not limited to medical devices (e.g. pacemakers, AICD, etc.) and other foreign bodies.
- 3.2.4 Known severe allergic reaction to Gadolinium-based contrast agents.
- 3.2.5 Patients with sickle cell disease and patients with other hemolytic anemias (low red blood count in body).
- 3.2.6 Patients with uncontrollable claustrophobia, sever lower back pain, and uncontrollable tremors, to the point that it would render them unable to tolerate an MRI study.

**4.0 TREATMENT PLAN**

**4.1 Treatment Dosage and Administration**

Not applicable.

**4.2 Toxicities and Dosing Delays/Dose Modifications**

Not applicable.

**4.3 Concomitant Medications/Treatments**

Not applicable.

**4.4 Other Modalities or Procedures**

Subjects will undergo treatment, as determined by the referring physician.

**4.5 Duration of Therapy**

Not applicable for this study.

**4.6 Duration of Follow Up**

After the conclusion of the study, subjects will be followed through standard clinical examinations for the next 3 years or until demise, whichever occurs first.

**4.7 Removal of Subjects from Protocol Therapy**

Subjects will be removed from the study when any of the criteria listed in Section 5.5 apply. Notify the Principal Investigator, and document the reason for study removal and the date the subject was removed in the Case Report Form. The subject should be followed-up per protocol.

**4.8 Subject Replacement**

If a subject is withdrawn from the study based on any criteria listed in Section 5.5, prior to completion of T2 MRI session, another subject may replace them and should undergo the entire study protocol.

**5.0 STUDY PROCEDURES**

**5.1 Screening/Baseline Procedures**

Assessments performed exclusively to determine eligibility for this study will be done only after obtaining informed consent. Assessments performed for clinical indications (not exclusively to determine study eligibility) may be used for baseline values even if the studies were done before informed consent was obtained.

All screening procedures must be performed within 30 days prior to registration unless otherwise stated. The screening procedures include:

**5.1.1 *Informed Consent***

**5.1.2 *Medical history***

Complete medical and surgical history, specific history regarding infections, trauma, foreign bodies, medical devices, and implants.

**5.1.3 *Demographics***

Age, gender, race, ethnicity

**5.1.4 *Review subject eligibility criteria (RCC Subjects only)***

Subjects will receive Group II gadolinium based contrast agents (GBCA) such as Gadavist (generic Gadobutrol) or Dotarem (generic Gadoterate acid) in this study. The risk of nephrogenic systemic fibrosis (NSF) for Group II GBCA is so low that the current clinical guidelines from the American College of Radiology (ACR) for use of these agents consider optional the screening of patient renal function – these were updated in 2017 (<https://www.acr.org/Clinical-Resources/Contrast-Manual>). The concern for gadolinium deposition is also lower for Group II agents and not related to renal function (i.e. associated to multiple exposures).

Accordingly, patients receiving group II GBCA for clinical MRI are no longer screened for renal function impairment at UT Southwestern. Hence, a strict threshold based on renal function will not be applied to avoid gadolinium administration in patients enrolled in this study. Patients will be informed of the risks of gadolinium administration and offered to participate in the non-contrast portion of the MRI exam if preferred.

**5.1.5 *Review previous and concomitant medications***

**5.1.6 *Physical exam including vital signs, height and weight***

Vital signs (temperature, pulse, respirations, blood pressure), height, weight

**5.1.7 *Performance status (RCC Subjects only)***

Performance status evaluated prior to study entry.

**5.1.8 *Adverse event assessment***

Baseline adverse events will be assessed. See section 7 for Adverse Event monitoring and reporting.

**5.1.9 *Pregnancy test (for females of child bearing potential)***

See section 3.1.5.1 for definition.

**5.1.10 *Tumor assessment (RCC Subjects only)***

Tumor measurements will be performed at baseline to identify metastatic tumors of ≥2.0 cm in at least one dimension on MRI.

**5.2 *Procedures During Treatment***

All MR imaging will be performed during treatment.

**5.3 *Follow-up Procedures***

After the conclusion of the study, subjects will be followed through standard clinical examinations for the next 3 years or until demise, whichever occurs first.

#### 5.4 Time and Events Table

##### RCC Subjects

	Pre-study	Week 0 (T0) before initiation of anti-angiogenic therapy	Day 7±2 (T1)	Day 14±2 (T2)	T3	T4	T5	Follow-up (As indicated by clinical protocol)
Assessment	X							
Informed Consent	X							
History and PE	X							
Tumor Measurements	X							
MRI*		X	X	X	X	X	X	X

\*Clinically, metastatic RCC patients are imaged every 2-3 months after the initiation of anti-angiogenic therapy, since morphological (i.e. size) changes are not anticipated earlier. However, our preliminary experience has shown functional changes including perfusion as early as 2-weeks after the initiation of the treatment (19). T0, T1, and T2 sessions will be performed for this proposal, while T3, T4, and T5 will be performed along with the clinical imaging sessions. The research MR imaging may take approximately an additional 15 minutes per each imaging session, when done in conjunction with the clinical imaging. The T0, T1, and T2 research MR imaging sessions will be performed additionally for the purpose of this study, with each taking approximately one hour.

The ASL portion of the study does not require contrast. Clinically, the subjects will also receive gadolinium based contrast injection for the MRI study to measure the blood flow to the tumors. This is done at the clinical imaging time points of T3, T4, and T5. Similar to this, the contrast agent will also be administered during the research portion of the study at T0, T1 and T2 time points, to compare the blood flow measured with ASL-MRI.

MRI including ASL will be performed before, during and after the treatment, in a total of 6 MRI sessions until 7 months after the first session, or when progression is clinically indicated. Thereafter, patients will be followed through standard clinical examinations for the next 3 years or until demise, whichever occurs first.

##### Healthy Volunteers

	Pre-study	Week 0	Week 3±1 (T3)
Assessment	X		
Informed Consent	X		
History and PE	X		
Research MRI		X	X

#### 5.5 Removal of Subjects from Study

Subjects can be taken off the study at any time at their own request, or they may be withdrawn at the discretion of the investigator for safety, behavioral or administrative reasons. The reason(s) for discontinuation will be documented and may include:

- 5.5.1 Subject voluntarily withdraws from the study (follow-up permitted);
- 5.5.2 Subject withdraws consent (termination of study and follow-up);
- 5.5.3 Subject is unable to comply with protocol requirements;

- 5.5.4 Subject experiences toxicity that makes continuation in the protocol unsafe;
- 5.5.5 Subject becomes pregnant (pregnancy to be reported along same timelines as a serious adverse event) AND pregnancy prevents the subject to undergo follow up studies, then subject will be removed from the study.
- 5.5.6 Development of second malignancy that requires treatment, which would interfere with this study;
- 5.5.7 Lost to follow-up. *If a research subject cannot be located to document survival after a period of 2 years, the subject may be considered "lost to follow-up." All attempts to contact the subject during the two years must be documented and approved by the Data Monitoring Committee.*

## 6.0 Measurement of Effect

### 6.1 Antitumor Effect- Solid Tumors

This study is designed to monitor therapy response in metastatic RCC using MRI with both conventional methods and ASL. Hence, the standard clinical assessment will be performed using RECIST criteria with conventional MRI. The ASL defined therapy response is currently developmental and not yet defined. Based on prior studies, a coefficient of variance (COV) of 7% was observed in ASL measured perfusion within the same subject imaged at two different time points (21). Thus, we will use a threshold of >10% difference in ASL measured perfusion compared to baseline to define ASL measured therapy response.

Response and progression will be evaluated in this study using the new international criteria proposed by the Response Evaluation Criteria in Solid Tumors (RECIST) Committee [JNCI 92(3):205-216, 2000]. Changes in only the largest diameter (unidimensional measurement) of the tumor lesions are used in the RECIST v1.1 criteria.

#### 6.1.1 Disease Parameters

Measurable disease. Measurable lesions are defined as those that can be accurately measured in at least one dimension (longest diameter to be recorded) as  $\geq 20$  mm with MRI. All tumor measurements must be recorded in millimeters (or decimal fractions of centimeters).

Note: Previously irradiated lesions are non-measurable except in cases of documented progression of the lesion since the completion of radiation therapy.

Non-measurable disease. All other lesions (or sites of disease), including small lesions (longest diameter  $< 20$  mm with MRI), are considered non-measurable disease. Bone lesions, leptomeningeal disease, ascites, pleural/pericardial effusions, lymphangitis cutis/pulmonis, inflammatory breast disease, abdominal masses (not followed by CT or MRI), and cystic lesions are all non-measurable.

Target lesions. All measurable lesions up to a maximum of 3 lesions per organ and 6 lesions in total, representative of all involved organs, should be identified as **target lesions** and recorded and measured at baseline. Target lesions should be selected on the basis of their size (lesions with the longest diameter) and their suitability for accurate repeated measurements (either by imaging techniques or clinically). A sum of the longest diameter (LD) for all target lesions will be calculated and reported as the baseline sum LD. The baseline sum LD will be used as reference by which to characterize the objective tumor response.

Non-target lesions. All other lesions (or sites of disease) including any measurable lesions over and above the 6 target lesions should be identified as **non-target lesions** and should also be recorded at baseline. Measurements of these lesions are not required, but the presence or absence of each should be noted throughout follow-up.

#### **6.1.2 Methods for Evaluation of Measurable Disease**

All measurements should be taken and recorded in metric notation using a ruler or calipers. All baseline evaluations should be performed as closely as possible to the beginning of treatment and never more than 28 days before the beginning of the treatment.

The same method of assessment and the same technique should be used to characterize each identified and reported lesion at baseline and during follow-up. Imaging-based evaluation is preferred to evaluation by clinical examination when both methods have been used to assess the antitumor effect of a treatment.

MRI should be performed with cuts of 10 mm or less in slice thickness contiguously.

#### **6.1.3 Response Criteria**

##### **6.1.3.1 Evaluation of Target Lesions**

Complete Response (CR): Disappearance of all target lesions, determined by two separate observations conducted not less than 4 weeks apart. There can be no appearance of new lesions.

Partial Response (PR): At least a 30% decrease in the sum of the longest diameter (LD) of target lesions, taking as reference the baseline sum LD. There can be no appearance of new lesions.

Progressive Disease (PD): At least a 20% increase in the sum of the LD of target lesions, taking as reference the smallest sum LD recorded since the treatment started, or the appearance of one or more new lesions.

Stable Disease (SD): Neither sufficient shrinkage to qualify for PR nor sufficient increase to qualify for PD, taking as reference the smallest sum LD since the treatment started.

##### **6.1.3.2 Evaluation of Non-Target Lesions**

Complete Response (CR): Disappearance of all non-target lesions and normalization of tumor marker level.

Incomplete Response/Stable Disease (SD): Persistence of one or more non-target lesion(s) and/or maintenance of tumor marker level above the normal limits.

Progressive Disease (PD): Appearance of one or more new lesions and/or unequivocal progression of existing non-target lesions

##### **6.1.3.3 Evaluation of Best Overall Response**

The best overall response is the best response recorded from the start of the treatment until disease progression/recurrence (taking as reference for progressive disease the smallest measurements recorded since the

treatment started). The subjects best response assignment will depend on the achievement of both measurement and confirmation criteria.

Target Lesions	Non-Target Lesions	New Lesions	Overall Response	Best Response for this Category Also Requires:
CR	CR	No	CR	≥4 wks. confirmation
CR	Non-CR/Non-PD	No	PR	≥4 wks. confirmation
PR	Non-PD	No	PR	
SD	Non-PD	No	SD	documented at least once ≥4 wks. from baseline
PD	Any	Yes or No	PD	no prior SD, PR or CR
Any	PD*	Yes or No	PD	
Any	Any	Yes	PD	

* In exceptional circumstances, unequivocal progression in non-target lesions may be accepted as disease progression.
 
Note: Subjects with a global deterioration of health status requiring discontinuation of treatment without objective evidence of disease progression at that time should be reported as “symptomatic deterioration”. Every effort should be made to document the objective progression even after discontinuation of treatment.
				

Note: If subjects respond to treatment and are able to have their disease resected, the patient's response will be assessed prior to the surgery.

#### 6.1.4 Duration of Response

Duration of overall response: The duration of overall response is measured from the time measurement criteria are met for CR or PR (whichever is first recorded) until the first date that recurrent or progressive disease is objectively documented (taking as reference for progressive disease the smallest measurements recorded since the treatment started).

The duration of overall CR is measured from the time measurement criteria are first met for CR until the first date that recurrent disease is objectively documented.

Duration of stable disease: Stable disease is measured from the start of the treatment until the criteria for progression are met, taking as reference the smallest measurements recorded since the treatment started.

#### 6.1.5 Progression-Free Survival

Progression-free survival (PFS) is defined as the duration of time from start of treatment to time of progression.

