## STUDY SUMMARY

Title	A Prospective Study to Evaluate Quantitative Non-Contrast Perfusion using Arterial Spin Labeled MR Imaging for Assessment of Therapy Response in Metastatic Renal Cell Carcinoma
Short Title	Quantitative MRI for therapy response assessment in metastatic RCC
Protocol Number	STU 032018-078
Phase	N/A
Methodology	Prospective study to evaluate quantitative MRI metrics for the assessment of treatment response
Study Duration	48 months
Study Center(s)	Single-center
Objectives	To prospectively determine whether ASL-measured perfusion can identify treatment response earlier than the currently used RECIST criteria.
Number of Subjects	90 (40 subjects with RCC and 50 healthy volunteers)
Diagnosis and Main Inclusion Criteria	Diagnosis: Locally advanced or metastatic renal cell carcinoma Main Inclusion Criteria: Patients with histologically proven clear cell RCC, scheduled to undergo anti-angiogenic treatment or immunotherapy (IO) who are 18 years of age and older and have no contraindication to MRI.
Study Product(s), Dose, Route, Regimen	N/A
Duration of administration	N/A
Reference therapy	N/A
Statistical Methodology	Primary end points for this study will include the absolute days of time to disease progression, progression free survival (PFS) and overall survival (OS) as well as disease status (progression versus not) at 7 months post treatment initiation. Progression will be determined according to the clinical RECIST criteria. One-sample correlation test will be used to determine the correlation between change in ASL measured tumor perfusion during and immediately after treatment and time to progression, and the correlation between change in ASL measured tumor perfusion and the corresponding tumor size change. The correlations will be measured and compared using Pearson's correlation coefficient along with 95% confidence interval. PFS and OS will be correlated with baseline perfusion and post-treatment changes at T1, T2 and T3 compared to baseline using univariable and multivariable Cox regression models. Univariable and multivariable logistic regression models will be used to predict responders from non-responders (progression versus not at 7 months) with ASL measurements at baseline and at earlier time points (T1 and T2) alone, and in combination with other MR imaging metrics.

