#### **2.2 Secondary Objectives**

- 2.2.1 To determine the correlation between ASL-measured baseline perfusion and the treatment response (PFS, OS).
- 2.2.2 To determine the correlation between post-treatment changes in ASL-measured perfusion at T1, T2 and T3 compared to baseline and the treatment response (PFS, OS).
- 2.2.3. To predict responders from non-responders (progression versus not at 7 months) with measurements at baseline and at earlier time points (T1 and T2) using:
  - a. ASL-measured perfusion alone
  - b. ASL-measured perfusion in combination with other MR imaging metrics such as diffusion weighted imaging (DWI) derived apparent diffusion coefficient (ADC), and chemical exchange saturation transfer (CEST) measured CEST effect.

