**10.0 STATISTICAL CONSIDERATIONS**

**10.1 Study Design/Study Endpoints**

This is a prospective, single-centered study, designed to address the following primary objective:

1. To determine whether ASL-measured perfusion can identify treatment response (time to progression) earlier than the currently used RECIST criteria (tumor size).  
*Hypothesis: Greater reduction in ASL measured tumor perfusion during and immediately after treatment is a marker of tumor responsiveness prior to size changes.*

Primary end points for this study will include the absolute days of time to disease progression, PFS and OS as well as disease status (progression versus not) at 7 months post treatment initiation. Progression will be determined based on clinically accepted RECIST criteria (20).

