**10.3 Data Analyses Plans**

The perfusion difference images and the absolute quantified images will be converted to DICOM and transferred to a DICOM database (e.g. iPACS, OsiriX). A semi-automated segmentation algorithm and region of interest (ROI) based measures will be performed to extract perfusion measures. Percentage changes in perfusion within each ROI will be calculated at each follow-up MRI compared to the baseline image. The semi-automated tumor ROIs will be compared to expert segmentation by [name] in all cases, who will also supervise the trainee (to be recruited) in the analysis. Additionally, morphological changes will also be calculated according to RECIST and 10% reduction in the sum of the largest diameters (20).

Among patients with disease progression, one-sample correlation test will be used to determine the correlation between change in ASL measured tumor perfusion during and immediately after treatment and time to progression, and the correlation between change in ASL measured tumor perfusion during and immediately after treatment and the corresponding tumor size change. The correlations will be measured and compared using Pearson's correlation coefficient along with 95% confidence interval. PFS and OS will be correlated with baseline perfusion and post-treatment changes at T1 and T2

compared to baseline using univariable and multivariable Cox regression models. We used PFS at 7 months as a cutoff point to divide patients into “responders” versus “non-responders” in this study. Univariable and multivariable logistic regression models will be used to predict responders from non-responders with ASL measurements at baseline and at earlier time points (T1 and T2) alone, and in combination with other MR imaging metrics. The statistical analysis will also be performed separately for male and female subjects to evaluate sex as a biological variable.

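### PFS stops at RECIST progression, so death without documented progression is not a PFS event and has no non-responder rule at 7 months

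*Combined protocol and SAP*

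**What the plan says.** Section 6.1.5 is the only place where PFS is defined: "Progression-free survival (PFS) is defined as the duration of time from start of treatment to time of progression". Section 2.4 says how progression is judged: "Progression will be determined based on the clinically accepted RECIST criteria". The criteria in 6.1.3 concern lesions; death is not among them.

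The study summary and section 10.1 name as primary end points the "absolute days of time to disease progression, PFS and OS as well as disease status (progression versus not) at 7 months", so time to progression and PFS stand there as two endpoints. Time to progression has no definition of its own. Section 2.4 lists only PFS and OS as primary and adds that "disease status (progression versus not) at 7 months and survival (dead or alive) at 24 months post-treatment initiation will also be documented".

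The 7-month outcome appears in two forms. The summary, objective 2.2.3, 2.4 and 10.1 use progressed or not progressed. Section 10.3 says "We used PFS at 7 months as a cutoff point to divide patients into" responders and non-responders. PFS and OS go into Cox models, and the 7-month split goes into logistic models. No event or censoring rule is given for either.

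Section 6.1.3.3 recognises symptomatic deterioration without objective progression and asks that "Every effort should be made to document the objective progression even after discontinuation of treatment". It does not say how such a patient enters PFS if progression is never documented.

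**The concern.** PFS normally counts death from any cause as an event. Here the written definition leaves it out, which has three consequences.

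- **Cox models (objectives 2.2.1 and 2.2.2).** A death without documented progression can only be a non-event, in practice a censored time. Such censoring is probably informative, since patients who deteriorate and die between scans are unlikely to share the future risk of those still followed. That is a judgement; the documents give no data on it.
- **Duplicate endpoint.** As defined, PFS measures the same interval as time to progression, so two listed primary endpoints collapse into one.
- **Logistic models (objective 2.2.3).** The progressed-or-not wording puts an early death with the responders. The section 10.3 wording, read with 6.1.5, leaves it unclassified. Neither makes it a non-response.

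The perfusion hazard ratios and the 7-month classifier would therefore depend on an unstated choice about some of the worst outcomes. With 40 patients, that choice could be made after the data are seen. Such deaths are plausible: section 3.1 admits locally advanced or metastatic disease with ECOG status up to 2, and clinical imaging is every 2 to 3 months (section 1.4).

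**Working it through.** **1. The plan's own figure.** Section 10.2 claims more than 95% power for a correlation of 0.75 with about 20 progressors, two-sided 0.05. By Fisher's z:

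power = Φ(atanh(0.75) × √(20 − 3) − 1.96) = Φ(0.973 × 4.123 − 1.96) = Φ(2.05) = 98.0%.

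Simulation of the t-test on Pearson's r (200,000 runs) gives 98.4%. The claim reproduces. The test concerns time to progression among progressors, so the PFS definition does not enter it.

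**2. Where a death at, say, month 4 without documented progression would fall.**

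| Place | Rule as written | Result for this patient |
|---|---|---|
| 6.1.5, used in the Cox models of 10.3 | interval ends at progression | no PFS event; no censoring rule |
| Summary, 2.2.3, 2.4, 10.1 | progressed or not at 7 months | literally not progressed, so a responder |
| 10.3 | PFS at 7 months, with PFS as in 6.1.5 | unclassified |
| 2.4 | dead or alive at 24 months | dead, but not linked to the 7-month status |

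**3. Size at 7 months.** Inputs from section 10.2: 40 patients, about 20 expected to progress by 7 months, hence about 20 not. The number of deaths without documented progression by 7 months, k, is not given. I assume 1 to 4; at k = 0 nothing changes. Such deaths may come (a) from the 20 expected non-progressors or (b) from the 20 expected progressors.

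| k | (a) share of labelled responders, k/20 | (b) share, k/(20 + k) |
|---|---|---|
| 1 | 5.0% | 4.8% |
| 2 | 10.0% | 9.1% |
| 3 | 15.0% | 13.0% |
| 4 | 20.0% | 16.7% |

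Under (a), counting death raises the 7-month PFS events from 20 to 20 + k, that is 21 to 24. The non-responder share rises from 20/40 = 50% to between 21/40 = 52.5% and 24/40 = 60%.

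**4. Effect on the classifier.** Let f be the fraction of labelled responders whose perfusion is distributed like that of non-responders. Then

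observed AUC = (1 − f) × true AUC + f × 0.5.

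| Assumed true AUC | f = 5% | f = 10% | f = 20% |
|---|---|---|---|
| 0.70 | 0.690 | 0.680 | 0.660 |
| 0.80 | 0.785 | 0.770 | 0.740 |
| 0.90 | 0.880 | 0.860 | 0.820 |

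Under (b) the loss is slightly smaller: with k = 4, 0.833 × 0.80 + 0.167 × 0.5 = 0.75.

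**5. Cox models.** I give no percentage. Total events over the roughly three-year follow-up are not stated, so the share of missed events cannot be worked out.

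**The case against.** The strongest reply is that everyone reads PFS as including death, so 6.1.5 is loose wording and 10.3 in its ordinary sense would make a patient dead by 7 months a non-responder. Listing time to progression and PFS side by side suggests the authors meant two quantities. That is a fair guess at intent, but the protocol gives an explicit definition and the ordinary reading contradicts it. The progressed-or-not wording elsewhere also points the other way.

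Several narrower points stand:

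- The identity of PFS and time to progression is inferred, because the latter has no stated start point. It concerns only the summary and 10.1.
- Vital status at 7 months can be derived from OS. The gap is a rule, not data.
- The death count, the true AUC and the resemblance to non-responders are all assumptions; deaths from other causes need not fit the last. The denominator of 20 is approximate and assumes every patient enters the model.
- Clinically prompted MRI, progression in non-target lesions and the effort to document progression will keep such deaths few. They give no rule for those that remain.
- The primary objective and sample size rest on the progressor correlation. If deaths came out of the expected 20 progressors, 19 to 16 would remain and power would be 97.3% to 93.9%. That loss comes from the deaths themselves, not from how PFS is worded.

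**Conclusion.** The concern holds. As written, PFS omits death and has no censoring rule. No section makes death by 7 months a non-response, and the wording used most often would class it as response. This follows from the text and needs no assumption.

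The size is conditional. Each such death by 7 months is about 5% of the labelled responders, and 1 to 4 of them amount to 5–20% (4.8–16.7% if drawn from expected progressors). An assumed AUC of 0.80 would then read about 0.785 to 0.74 under (a), if the misplaced patients look like non-responders. The effect on the hazard ratios cannot be quantified from the documents. What is affected is PFS as a listed primary endpoint, the Cox models for 2.2.1 and 2.2.2, and the logistic models for 2.2.3. The point should be corrected before analysis, but it does not undermine the sample size.

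**What to change.** - **6.1.5:** define PFS as the time from start of treatment to first RECIST progression or death from any cause, whichever comes first. Censor patients alive and progression-free at the last evaluable tumour assessment.
- **2.2.3 and 10.3:** define a 7-month non-responder as a patient with progression or death by 7 months, and use the same wording in the summary, 2.4 and 10.1.
- **Time to progression:** keep it as a separate endpoint with its own start point and a stated handling of death (censored or competing event).
- **Optional:** treat patients alive but of unknown 7-month status as missing in the logistic model, not as responders, with one sensitivity analysis.

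The cost is low: a short paragraph in 6.1.5 and 10.3, matching wording elsewhere and, if the optional item is adopted, one extra analysis. No new data are needed, since death dates are already required for OS.
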